4.1. Study Flow Diagram

5. PHARMACOTHERAPY INTERVENTIONS

5.1. Varenicline (VAR)

Varenicline will be used in this study for oral administration in two strengths:

- a 0.5 mg capsular biconvex, white to off-white, film-coated tablet debossed with "Pfizer" on one side and "CHX 0.5" on the other side

- a 1 mg capsular biconvex, light blue film-coated tablet debossed with "Pfizer" on one side and "CHX 1.0" on the other side.

Varenicline tablets will be provided by Pfizer and supplied in blister packs and should be stored at 77°F, with excursions permitted to 59–86°F.

5.2. Naltrexone (NTX)

NTX will be prepared by the UCLA pharmacy and packed into opaque capsules with 50 mg of riboflavin (B2) to aid in medication compliance procedures. Naltrexone will be provided for oral administration in three strengths:

- 12.5 mg capsules will be provided for the first 3 days, packaged in a blister pack.
- 25 mg capsules will be provided for days 4-7, packaged in a blister pack.
- 50 mg capsules will be provided for weeks 2-14 in amber child-resistant medication bottles.

5.3. Placebo (PLA)

Placebo tablets will be prepared by the UCLA pharmacy and packed into opaque capsules with 50mg of riboflavin (B2) to assess for medication compliance. Placebo capsules will be identical in appearance to Naltrexone tablets and will be provided in a blister pack for week 1 and in amber child-resistant medication bottles for weeks 2-14.

5.4. Study Medication Blinding

Naltrexone tablets and placebo tablets will be identically matched in appearance and the medication labels will not reveal the drug identity. The PI or designated approved study physician will make the decision to un-blind the identity of the study medication in the event that the study blind needs to be broken to make medical decisions regarding subject treatment (i.e. if necessary to assess AEs or SAEs for expedited reporting). Proper regulatory authorities will be notified if unblinding is required for a participant due to safety concerns.

5.5. Study Medication Handling

5.5.1. Medication Dispensing

At the medication titration visit, study medication will be dispensed as prescribed by the study physician. Drug accountability and compliance will be performed by the research staff at each clinic visit. The subject will be asked to bring all study medication and packaging (used and unused) to each subsequent visit for accountability. When study medications are dispensed, the subject will also be given a Medication Information Sheet for Varenicline and Naltrexone.

5.5.2. Medication Accountability

The PI or designated study personnel will maintain a log of the receipt of all study medications and record of dispensing of all study medications to the subject. Medication for each subject will be inventoried and accounted for throughout the trial. The PI or designated staff will count the tablets remaining at the end of the study and record the tablet count on the appropriate drug accountability form. Subject compliance with medication will be assessed by comparing unused tablet count to dispensing logs and dosing records (number of tablets dispensed, number of tablets prescribed, versus the number returned). Subjects will also be asked to account for any missing tablets. If the medication is not returned, the subject will be asked to report daily drug self-administration.

5.5.3. Medication Compliance

Pill counts will be conducted at each visit. In addition, the naltrexone study medication will be packed into opaque capsules with 50 mg of riboflavin (B2). A urine sample will be tested for riboflavin content by examining it under an ultraviolet light at each visit. In addition, 20% of all participants may be randomly selected for a serum verification of medication content (varenicline and naltrexone) at each follow-up.

6. BEHAVIORAL INTERVENTIONS

6.1. Initial Smoking Cessation Counseling Session

All subjects will receive one smoking cessation counseling session to take place during week 2 of the medication protocol. Per published guidelines, session will focus on problem solving and relapse prevention skills training. All study staff will be equipped to deliver this intervention through training and ongoing supervision by the PI, a licensed clinical psychologist. Subjects will be encouraged to maintain abstinence and to take the study medication. However, eligibility to continue in the study or receive study compensation will not be affected if participants do not maintain abstinence and/or are not compliant with the medication. This session will last approximately 45 minutes.

6.2. Follow Up Smoking Cessation Counseling Sessions

Participants will also receive brief cessation counseling at each follow-up visit focusing on topics as described above.

6.3. Rethinking Drinking Program

In addition, all participants will be encouraged to complete the “Rethinking Drinking” program online (<http://rethinkingdrinking.niaaa.nih.gov/default.asp>) while in the study and will discuss their drinking with the counselor.

7. STUDY PROCEDURES

7.1. Recruitment of Subjects

Mass media advertisements will be placed in local newspapers and on local radio stations in the greater Los Angeles metropolitan area. Targeted recruitment will also take place through existing research databases from the [name] and [name] laboratories (each laboratory has contact information for over 500 daily smokers who completed previous studies and are interested in being called about future studies) as well as through the UCLA primary care clinics. In addition, we will employ snowball sampling. Participants who voluntarily agree will have an opportunity to forward a text message providing brief information about the study (drafted by the study team) to up to 5 acquaintances. Participants will earn an additional \$1 in compensation for each text message they send, up to \$5. Men and women of all ethnic backgrounds will be recruited into the study. We expect that the study will reflect the ethnic diversity of Los Angeles County. Given that the requirement of ≥ 5 cig/day may disproportionately exclude females and ethnic minorities, targeted recruitment will be carried out to ensure a balanced representation of these groups in our study.

7.2. Eligibility Criteria

7.2.1. Inclusion Criteria

To be included in the study, participants **must**:

1. Be treatment-seeking for smoking cessation and have a desire to reduce or quit drinking
2. Be between the ages of 21 and 65
3. Be able to provide informed consent
4. Smoke 5 or more cigarettes per day for the past year
5. Currently drink heavily according to the National Institute on Alcohol Abuse and Alcoholism (NIAAA) guidelines: for men, > 14 drinks per week or ≥ 5 drinks per occasion at least once per month over the past 12 months; for women, > 7 drinks per week or ≥ 4 drinks per occasion at least once per month over the past 12 months
6. Pass the physical exam and associated laboratory tests, as determined by study physician.

7.2.2. Exclusion Criteria

To be included in the study, participants **must not**:

1. Have clinically significant alcohol withdrawal, indicated by a score ≥ 10 on the Clinical Institute Withdrawal Assessment for Alcohol (CIWA-Ar) and assessed at the in-person screening visits
2. Have lifetime DSM-V diagnosis of schizophrenia, bipolar disorder, a psychotic disorder, or any other psychiatric disorder as determined by the clinical interview

3. Have major depressive disorder within the past year requiring treatment as determined by the clinical interview using DSM-V criteria
4. Have a current DSM-V diagnosis of a substance use disorder, other than for alcohol or nicotine, as determined by the clinical interview
5. Have a prior history of taking FDA approved medications (i.e. varenicline or bupropion) for smoking cessation
6. Be currently using any forms of nicotine replacement therapy (past use is acceptable)
7. Have a serious medical illness (significant cardiovascular disease; uncontrolled hypertension; hepatic or renal disease) that would contraindicate participation, as determined by the study physician
8. Be currently taking opioid pain medications or any form of opioid agonist maintenance therapy (such as methadone or buprenorphine)
9. Be currently taking any psychoactive medications that would indicate serious or unstable mental illness, such as certain antidepressants, mood stabilizers or anti-seizure medications, sedatives-hypnotics, anxiolytics, stimulants, antipsychotics, as determined by the study physician.
10. Have self-reported use of cocaine, methamphetamine, heroin or other illicit drugs in the previous 60 days, verified by urine toxicology screen
11. For women, must not be pregnant (as indicated by self-report or a positive pregnancy test at any study visit), nursing, or planning to become pregnant while taking part in the study, and must agree to one of the following methods of birth control, unless she or partner are surgically sterile:
 - Oral contraceptives
 - Contraceptive sponge
 - Patch
 - Double barrier
 - Intrauterine contraceptive device
 - Etonogestrel implant
 - Medroxyprogesterone acetate contraceptive injection
 - Complete abstinence from sexual intercourse
 - Hormonal vaginal contraceptive ring

7.3. Screening Period

7.3.1. Telephone Screen

Individuals who call the lab (in response to flyers and advertisements) expressing interest in the study will receive detailed information about the study procedures, and if they remain interested they will complete a telephone screen performed by a trained research assistant for self-reported inclusion and exclusion criteria. Those who appear eligible will be invited to the laboratory for an initial in-person screening session.

7.3.2. Initial Screening Visit

Prior to conducting any research related procedures, research staff will conduct the informed consent process which details the procedures to take place during the screening visit. Informed consent will be a three part process. First, participants will be asked to read and provide verbal consent for breathalyzer. If the breathalyzer is above 0.000, the visit will be stopped and the participant will not be compensated. The participant will be given an opportunity to reschedule the visit for another day. If the breathalyzer test is negative, the written informed consent form will be reviewed and signed by the participant and study staff outlining procedures for the initial screening visit. A second written consent form will be reviewed and signed in the presence of the study physician at the medical screening visit if the participant is found eligible to continue to that visit.

At the initial screening visit, subjects will be asked to provide a urine sample for cotinine verification of smoking status and test for drugs of abuse and pregnancy (if female), be given a breath test of CO level and will complete a series of smoking and individual differences measures (described in detail below). This visit should take 1.5 to 2 hours.

Following the initial in-person screening, the study coordinator will meet with the PI to determine if the participant is eligible to continue to the medical screening based on study inclusion/exclusion criteria.

7.3.3. Medical Screening Visit

Those participants who appear to be eligible after the initial screening visit, will then be scheduled for a second screening visit to take place at the UCLA Clinical and Translational Research Center (CTRC). This visit will be conducted by the study physician and will start with a breathalyzer test. If the breathalyzer is above 0.000, the visit will be stopped and the participant will not be compensated. The participant will be given an opportunity to reschedule the visit for another day. If the breathalyzer test is negative, the physician will conduct the second written (experimental) consent, medical history interview, physical exam, Comprehensive Metabolic Panel including liver function tests (LFTs) and blood chemistry, and EKG to screen for medical conditions that contraindicate taking naltrexone and/or varenicline. In addition, CO levels, and urine drug screen tests will be repeated. The study physician will review each participant's medical history, vital signs, weight, review of systems, and laboratory tests, including liver function tests (LFTs), drug screen, chemistry screen, and urine pregnancy screen to determine if it is medically safe for the participant to take the study medication.

Any subject who is excluded from the study will be compensated for their time in the screening session and will be offered referrals for smoking cessation treatment in the community.

7.4. Medication Titration/Stabilization Period

7.4.1. Randomization and Medication Titration Visit

Participants who are eligible after the medical screening visit will be scheduled to come into the lab to be randomized and start study medication. Subjects will be urn randomized to one of two medication groups. Urn randomization will be used to balance the two medication groups by gender, number of cigarettes per day, and drinks per drinking day. At this visit, a quit date will be set for day 14 of the medication titration/stabilization regimen.

Female participants will be asked about their menstrual cycle and reproductive status and will answer questions about hormonal responses and symptoms (see Schedule of Assessments). In addition, female participants of child-bearing potential will provide a saliva sample for testing of progesterone and estradiol levels and urine will be tested for surges in luteinizing hormone (LH).

7.4.1.1. Medication Titration Schedule

Titration Day	VAR	NTX/PLA
1	.5 mg once per day	12.5 mg once per day
2	.5 mg once per day	12.5 mg once per day
3	.5 mg once per day	12.5 mg once per day
4	.5 mg twice per day	25 mg once per day
5	.5 mg twice per day	25 mg once per day
6	.5 mg twice per day	25 mg once per day
7	.5 mg twice per day	25 mg once per day
8+	1 mg twice per day	50 mg once per day

All pills will be matched in number of pills and packaging across the two medication conditions (VAR + PLA and VAR + NTX). Participants will be asked to take the study medications for a period of 14 weeks and will complete regular follow-ups.

7.4.2. Titration Follow Up Telephone Contact

The study physician will contact the participant via telephone once during the first week of the medication titration period to assess for side effects/adverse events and the potential need for dosage adjustments.

7.4.3. Initial Counseling Session

All subjects will receive one smoking cessation counseling session to take place during week 2 of the medication titration period. This session will last approximately 45 minutes, and will focus on preparation for the upcoming quit date.

7.4.4. Brain Imaging Session

Participants found to be eligible for an MRI, as determined by the MRI Safety Screening form, will be asked to complete a brain imaging session after 9-12 days of taking the medication.

Participants will be asked to abstain from drinking alcohol prior to coming into the lab for the brain imaging session, which will be verified through a breathalyzer. Only participants with a blood alcohol concentration of zero will be allowed to complete the scanning visit. Female participants will be given a pregnancy test to make sure that they are not pregnant. We will also collect a urine sample on that day to verify compliance with the study medication. We will then ask participants to fill out a few questionnaires including information about your use of alcohol and tobacco.

After the initial questionnaires, participants will receive some training on how to complete questionnaires in the scanner. The scanning will be performed at the Brain Mapping Center or at the Center for Cognitive Neuroscience, both located on the UCLA campus. They will be asked to lie down on a padded table, with their head placed in the center of a large, metal doughnut-shaped magnet. While the machine is running, the participant will hear loud banging noises and will be offered earplugs to reduce the noise made by the magnet. Head and back support will also be provided to minimize discomfort. In the scanner, participants will watch brief videos of individuals smoking cigarettes or performing daily activities, such as driving and will view alcohol and neutral cues. They will also be asked to rate their urge to smoke cigarettes and drink after watching each of these videos and visual cues.

7.5. Medication Follow Up Period (Weeks 2, 4, 6, 8, 10, & 12)

Follow-up visits will occur at the UCLA Addictions Lab on weeks 4, 8, 12, 16, and 26. Telephone or in-person follow-up interviews will be conducted at weeks 2, 6 and 10. At each in-person follow up visit, participants will be asked to provide a urine specimen for cotinine level testing, perform an alcohol breathalyzer test, expired alveolar carbon monoxide (CO) levels test and complete measures as described in the Schedule of Assessments (Appendix 2). In addition, urine specimen will be assessed for pregnancy and LH and saliva sample will be collected to test for progesterone and estradiol levels monthly for female participants. Blood chemistry labs will be drawn at the last medication follow up visit at week 12. Participants will be asked to bring all study medication and used packaging to each visit to assess for medication compliance and will be dispensed study medication to last until the next scheduled visit.

Female participants will be asked about their menstrual cycle and reproductive status and will answer questions about hormonal responses and symptoms (see Schedule of Assessments). In addition, female participants of child-bearing potential will provide a saliva sample for testing of progesterone and estradiol levels and urine will be tested for surges in luteinizing hormone (LH).

7.6. Post-Medication Follow Up Period (Weeks 16 & 26)

At 16 and 26 weeks post quit date, participants will return to the UCLA Addictions Lab for post-medication follow up visits. At each visit, participants will be asked to provide a urine specimen for cotinine level testing, perform an alcohol breathalyzer test, expired alveolar carbon monoxide (CO) levels test and complete measures as described in the Schedule of Assessments (Appendix 2). Female participants of child-bearing potential will also be tested for pregnancy, LH levels and progesterone and estradiol levels.

7.7. Dose-adjustment Criteria

Participants who discontinue study medication should still continue in the study, and complete all assessments as scheduled. Females who become pregnant during the course of the study will be instructed to immediately discontinue use of the study medication and the pregnancy will be reported per required regulatory guidelines. Participants will need to be removed from study medication if they have a serious illness or a disabling condition that precludes them from taking the medication. If the participant experiences any AEs that are considered study drug related and for which the study physician has determined that continuation of the study drug could be detrimental to the health of the subject, then drug will be immediately discontinued as described above.

7.8. Subject Withdrawal or Discontinuation Procedures

Participants have the right to withdraw consent and withdraw from the study at any time. In addition, the investigator may find it necessary to discontinue a participant for any reason, including the occurrence of an AE or noncompliance with the protocol. In the event that a participant withdraws or is discontinued from the study, the reason(s) for the discontinuation from the study will be recorded. A final follow up visit will be scheduled and collected if possible.

7.8.1. Stopping Criteria due to Safety Concerns

The following trial stopping rules have been established: If two subjects have unexpected serious life-threatening AEs (attempted/completed suicide, extreme psychosis, etc.) the study will be halted and the DSMB will determine if the study should continue or be terminated overall.

If at any time during study procedures, a participant develops any of the following stopping criteria, the study physician will abort study procedures, treat and/or observe the participant until stable, and discharge the patient from the study once stable with a 14-day post-discharge outpatient follow-up visit to complete additional safety assessments:

1. Abnormalities on liver function tests >3 times the baseline levels or any other clinically significant lab values or AEs.

2. Pregnancy: Both NTX and VAR are classified as Pregnancy Category C drugs by the FDA, and the drugs should only be used during pregnancy if the potential benefit justifies the potential risk to the fetus. As such, females who become pregnant during the course of the study will be instructed to discontinue the medication; the study physician will request a release of information to discuss the use study medication with their obstetrician. The participant will be followed through her pregnancy.
3. Psychiatric crises, including but not limited to the following:
 - a. Acute psychosis (hallucinations, impaired reality testing, paranoid ideation, etc.) requiring medication and/or hospitalization or intensive outpatient intervention;
 - b. Suicidal or homicidal ideation that results in a credible threat of violence directed at oneself or others;
 - c. Hospitalization for psychiatric symptoms
4. A positive urine drug screen indicating illicit use of cocaine, methamphetamine, opiates, or other abused drugs at any visit during the trial.
5. Self-reported use of contraindicated medications (as listed in the inclusion/exclusion criteria)

Participants who report adverse reactions will be individually evaluated by the study physician. All participants will be clearly instructed that they may stop the study medication at any time. Upon physician evaluation, participants who reports either a severe side effect or any side effects that are not tolerable to them, whether severe or not, will be subjected to withdrawal by investigator and will be asked to discontinue the study medication immediately. In such cases, participants will be offered a follow-up visit with the study physician to re-evaluate symptoms upon discontinuation of the study medication.

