2.2. Varenicline: effective for smoking cessation and may reduce alcohol use

A number of pharmacological treatments have been developed for nicotine dependence. Nicotine replacement therapy appears to be modestly effective, presumably by decreasing withdrawal [34]. Bupropion is another medication with moderate effectiveness, although its mechanisms of action remain relatively unclear. It is thought that the effect of bupropion on dopamine, noradrenaline, or even its direct effects on nicotine receptors may be involved in its clinical efficacy [35]. More recently, varenicline has been approved for the treatment of tobacco dependence. Molecular studies have convincingly demonstrated that the $\alpha 4\beta 2$ subtype is necessary for nicotine dependence [36, 37]. Developed to address the critical role of $\alpha 4\beta 2$ in tobacco dependence, varenicline is a partial agonist at $\alpha 4\beta 2$ receptors. The putative mechanisms of action of varenicline stem from the stimulation of dopamine release (as a partial nicotine agonist) [38] and with its ability to block the binding of nicotine to its site (an antagonist effect), which in turn results in reductions in nicotine craving and reward [39]. At the behavioral level, varenicline-induced blockade of $\alpha 4\beta 2$ nAChRs reduces craving and withdrawal and attenuates the rewarding effects of smoking [39-43]. Functional neuroimaging studies found that varenicline increases activation of the dorsal anterior cingulate/medial frontal cortex, and dorsolateral prefrontal cortex during a working memory task [44] as well as during an emotional processing task [45]. Moreover, varenicline diminished smoking cue-elicited ventral striatum and medial orbitofrontal cortex responses compared to placebo [46]. Perhaps most importantly, a number of clinical trials found that varenicline is more effective than bupropion [10], superior to nicotine replacement therapy [47], and significantly more effective than placebo [10, 48-51] as a smoking cessation agent. As a result of this compelling clinical data, varenicline was advanced as a first line treatment for nicotine dependence [52]. It is to be noted, however, that abstinence rates on varenicline are about 43% at 12

weeks and 25% at one-year follow-up [53]. Thus, even though varenicline is superior to other treatments, there is a clear opportunity to improve upon these clinical outcomes, particularly among hard-to-treat sub-groups such as heavy drinking smokers.

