Combining Varenicline and Naltrexone for Smoking Cessation and Drinking Reduction

DATA ANALYSIS PLAN

NCT02698215

October 2018

Analyses were conducted in SAS Statistical Software Version 9.4. All analyses were of the intention-to-treat type. Since all participants took the first dose of the study medication under observation during the randomization visit, all participants were included in the subsequent analyses. The dichotomous primary outcome for smoking cessation at the 26-week follow up was analyzed using a Chi-Square test comparing smoking cessation rates for the two medication conditions. For the purpose of these analyses, all individuals who dropped out from the trial were considered to have returned to smoking, per guidelines for smoking cessation trials. For the drinking outcomes, all of which were continuous, a series of multilevel models, via Proc Mixed, were conducted for each outcome separately, during the 12-week treatment period and for the entire 26-weeks of the trial, which is consistent with pharmacotherapy trials for excessive drinking. These models tested whether the two medication groups differed in alcohol use over the 12-week medication period and across the entire 26-weeks of the trial. All models for drinking outcomes controlled for baseline drinking levels.

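### Section 7.7 keeps participants who stop drug in follow-up, but section 7.8.1 discharges them from the study for the same events, so week-26 smoking status may be lost and scored as smoking

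*Protocol*

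**What the plan says.** Protocol section 7.7 sets the general rule: "Participants who discontinue study medication should still continue in the study, and complete all assessments as scheduled". It goes on to name pregnancy, and drug-related adverse events that make continuing the drug harmful, as reasons to stop medication.

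Protocol section 7.8.1 lists stopping criteria for individual participants. Its lead-in says that on meeting any of them the physician aborts study procedures, treats or observes the participant, and then will "discharge the patient from the study once stable with a 14-day post-discharge outpatient follow-up visit". That visit is for additional safety assessments. The first criterion covers liver-test abnormalities "or any other clinically significant lab values or AEs", and the second is pregnancy. The closing paragraph of 7.8.1 says that participants with severe or intolerable side effects "will be subjected to withdrawal by investigator and will be asked to discontinue the study medication immediately".

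For anyone withdrawn or discontinued, section 7.8 adds: "A final follow up visit will be scheduled and collected if possible".

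The SAP tests 26-week smoking cessation with a chi-square test by intention to treat, and states that "all individuals who dropped out from the trial were considered to have returned to smoking". It does not define dropout and gives no other rule for missing smoking data.

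**The concern.** The same event can put a participant under two opposite instructions: stay and complete all assessments, or leave the study after one safety visit. Whichever section site staff follow decides whether a week-26 smoking status exists.

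If 7.8.1 is followed, the protocol gives up an outcome that 7.7 would have collected. A participant who was abstinent at week 26, but had been removed by the study physician, could then enter the primary test as a smoker. Counting missing as smoking is a usual convention for people who disappear. It is harder to defend when the protocol itself ends contact.

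Naltrexone versus placebo is the only drug difference between the arms, so unequal discharge for adverse events is plausible, although the documents do not quantify it. If discharge is unequal and some of those discharged would have been abstinent, the comparison is biased against the arm with more discharges.

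**Working it through.** **The text, set side by side**

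| Event | Section 7.7 | Section 7.8.1 | Does anything else secure week-26 status? |
|---|---|---|---|
| Drug-related adverse event | Stop drug, continue assessments | Discharge from study if clinically significant; 14-day safety visit | No. The section 7.8 final visit is conditional and not tied to week 26 |
| Pregnancy | Stop drug; general rule continues assessments | Lead-in discharges; criterion text stops drug and follows the pregnancy | No. Follow-up in 7.8.1 and 9.1 concerns the pregnancy, not smoking |
| Severe or intolerable side effect | Stop drug, continue assessments | Investigator withdrawal; unclear whether from drug or study | No. Only a physician visit to re-evaluate symptoms |

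The overlap has limits. Section 6.1 says that continuing in the study "will not be affected if participants do not maintain abstinence and/or are not compliant with the medication", so ordinary non-adherers stay. Section 9.38 lists urine drug screens only up to the titration visit. Section 9.6 schedules liver tests only at medical screening and week 12. Adverse events and pregnancy are therefore the main overlap.

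**Inputs for the size**

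- n = 137 per arm (protocol section 4).
- Background quit rates: section 2.2 says "abstinence rates on varenicline are about 43% at 12" weeks and 25% at one year. No 26-week rate is given.
- The documents state no discharge rate, target effect, alpha or power, so there is no figure in the plan to reproduce. The discharge rates, the 25% versus 41% scenario and two-sided alpha 0.05 are assumptions.

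**Formulas**

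Let p be an arm's true week-26 quit rate, d the share discharged and scored as smoking, and r the quit rate among those discharged relative to the arm's rate (0 = none would be abstinent, 1 = same as the arm).

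- Observed rate = p × (1 − d × r)
- Bias with no true effect = −p × r × (d_combination − d_control)
- Power = Φ{ [|p₁ − p₀| − 1.96 √(2p̄(1 − p̄)/n)] / √([p₁(1 − p₁) + p₀(1 − p₀)]/n) }

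**Bias with no true effect, in percentage points (r from 0 to 1)**

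| Gap in discharge | Participants (of 137) | p = 25% | p = 43% |
|---|---|---|---|
| 3 points | about 4 | 0 to −0.75 | 0 to −1.3 |
| 5 points | about 7 | 0 to −1.25 | 0 to −2.15 |
| 10 points | about 14 | 0 to −2.5 | 0 to −4.3 |

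For example, 0.43 × 1 × 0.05 = 2.15 points.

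**Power, illustrative 25% versus 41%**

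With complete follow-up, or with r = 0, power is 80.8%. Worked case, 5% versus 10% discharged at r = 0.5: control 0.25 × (1 − 0.025) = 0.2437; combination 0.41 × (1 − 0.05) = 0.3895; power 73.9%.

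| Discharged, control vs combination | r = 0.5 | r = 1 |
|---|---|---|
| 1% vs 2% | 79.5% | 78.2% |
| 2% vs 4% | 78.2% | 75.4% |
| 5% vs 5% | 79.3% | 77.7% |
| 3% vs 6% | 76.8% | 72.4% |
| 3% vs 8% | 74.6% | 67.6% |
| 5% vs 10% | 73.9% | 66.0% |
| 5% vs 15% | 68.0% | 52.4% |

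The equal-discharge row shows that part of the loss does not depend on any imbalance between arms.

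**The case against.** The strongest reply is that the conflict is narrow. It rests mainly on one lead-in sentence, which reads like a rule for acute events: abort procedures, treat, observe until stable. Most other criteria are of that kind, such as psychiatric crises and large liver-test rises. On that reading, ordinary drug-related adverse events stay under 7.7. The pregnancy criterion itself speaks only of stopping medication, and contraception is an entry condition, so cases should be few. The side-effect paragraph is mostly about medication, so its withdrawal may mean withdrawal from drug.

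The harm also needs a chain. The broad reading must be applied, no week-26 status obtained, the exit scored as dropout, and some of those discharged must be true quitters. The documents show none of these happening. Every rate is assumed. Both arms receive full-dose varenicline, so its adverse events are common to both. At low discharge rates the loss is small, about 1 to 3 points of power at r = 0.5. The r = 1 column is an upper bound, because it supposes that people removed for adverse events and now off drug quit as often as everyone else.

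Much of this stands, and it limits the size. It does not remove the problem. The 7.8.1 wording does not exclude the broad reading, and the lead-in covers pregnancy expressly. If staff can read the text either way, handling may differ from one participant to the next, which is itself a reason to settle it.

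**Conclusion.** The concern holds, as a point that should be fixed. Sections 7.7 and 7.8.1 give different instructions for drug-related adverse events and pregnancy, and following 7.8.1 as written gives up week-26 smoking status that 7.7 would have collected. Under the SAP's only missing-data rule, those exits would most naturally count as smoking, though the SAP does not say so.

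The size is uncertain because no discharge rate is given. If few are discharged, or almost none of them would have been abstinent, little or nothing is lost. With 5% versus 10% discharged and half the arm's quit rate among them, the illustrative power falls by about 7 points (80.8% to 73.9%). Larger losses need more discharges or a higher quit rate among those discharged.

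If discharge is commoner on naltrexone, the error is conservative: an understated effect and lost power. Drinking data collected before exit still enter the mixed models; only the Timeline Followback after exit is lost.

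**What to change.** - **Protocol 7.8.1, including its closing paragraph on adverse reactions:** state that these criteria end study medication and any unsafe study procedures, but not outcome follow-up, in line with 7.7.
- **Data collection:** obtain week-26 smoking status and the Timeline Followback from every randomised participant who has not withdrawn consent.
- **SAP:** define dropout, score the observed week-26 status whenever there is one, and count as smoking only those with none.
- **Reporting:** give investigator removals by arm and reason.

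Clinical stopping decisions do not change. The cost is wording in two documents and a few more contacts, at visits already planned for all 274 participants. Some of those taken off drug may decline. If participants have already left, reporting removals by arm and scoring any week-26 status already obtained can still be done at analysis.
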